9.0 STUDY PARAMETERS

Test/Observation	Prior to Study	Post Anastrozole	Post Lumpectomy
History	X		
Physical Examination	X		
Mammographic findings (suspicious for DCIS or early invasive breast cancer)	X		
MRI findings	X	X	
Ki-67	X (on core biopsy)		X
Confirm DCIS or early invasive breast cancer on pathology	X (on core biopsy)		Final pathological diagnosis
Assessment of Tumor Grade and Histologic Type	X(on core biopsy)		Final pathological diagnosis
ER/PR status	X(on core biopsy)		Confirm ER/PR status
IHC scores of markers of angiogenesis	X(on core biopsy)		IHC scores of markers of angiogenesis

10.0 CRITERIA FOR EVALUATION AND ENDPOINT DEFINITIONS

10.1 Absolute percent Ki-67 change pre anastrozole and post anastrozole as well as percentage of patients achieving less Ki-67 less than 10%

10.2 Histopathological response.

A complete response (CR) indicating the disappearance of the primary tumour; a partial response (PR) indicating a reduction of $\geq 50\%$; stable disease (SD) indicating a reduction of $< 50\%$ or increase in size of $< 25\%$; progressive disease (PD) indicating an increase in size of $\geq 25\%$.

The pathological CR will be evaluated by tumour excision and axillary node resection (in case of invasive breast cancer only). Two grading classifications will be utilised to evaluate the tumour response after chemotherapy. In the Chevallier classification, the absence of invasive tumour cells, or persistence of *in situ* disease, and negative axillary lymph nodes define a pathological CR. In the Sataloff classification, we have similar criteria for a pathological CR, but also observe the persistence of small clusters of widely dispersed cells in these cases.

We will correlate patients with degree of drop of Ki-67 with degree of pathological response

10.3 MRI is obtained at the base line and 4 weeks after anastrozole.

MRI characteristics pre and post anastrozole

10.4 IHC determination of markers of angiogenesis and ER, PR and pre anastrozole and post anastrozole expressed as IHC scores and percentage.

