Specific Aim 1: We hypothesize that a proliferative marker Ki-67 is reduced in patients with preinvasive (DCIS) and very early breast cancer treated with anastrozole. To establish reduction in Ki-67 as a primary surrogate endpoint to breast cancer risk reduction in patients treated with anastrozole we will measure Ki-67 before and after treatment with anastrozole. Consistent with this, it has been demonstrated by Geisler et al that patients with invasive breast cancer show a decrease in Ki-67 on lumpectomy/mastectomy samples when anastrozole is administered for few weeks prior to definitive surgery. In addition, there is a trend for a more profound suppression in those achieving an objective response. Ki-67 will be measured by routine immunohistochemistry.

Specific Aim 2: We hypothesize that histopathological tumor response will be demonstrated in 30-40 percent of patients with preinvasive (DCIS) and early invasive (less than 2 cm) breast cancer treated with anastrozole. The percent ability to reverse early breast cancer lesions in patients treated with anastrozole will be qualified as a secondary surrogate endpoint to breast cancer risk reduction. Consistent with this, it has been demonstrated that 30-40 percent of patients with invasive breast cancer show an infiltration of foamy macrophages and fibrosis on lumpectomy/mastectomy samples when chemotherapy is administered for few months prior to definitive surgery. Further, there is a trend for a more profound change in those achieving a complete clinical response. Importantly, a complete pathological response in these invasive breast cancer has been shown to correlate with improved disease free survival and overall survival in breast cancer patients. A corollary is that if reversibility of early carcinogenic lesions is reliably demonstrated in our present proposal, it would translate into chemoprevention of breast cancer.

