Angiogenesis plays a fundamental role in tumor growth and metastasis. Investigations by Teruyama et al. and Mastuyugin et al. have established a relationship between VEGF expression and p450 aromatase activity (Teruyama, 2001; Mastuyugin, 2002). We have previously shown that dynamic contrast enhanced MRI in conjunction with compartmental modeling may be used to assess the angiogenic status of tumors while enabling the study of both breasts (Su, 2002). Additionally, image based measurement techniques do not suffer from the errors due to tissue heterogeneity and use of limited spatial sampling imposed in methods such as histology. Furthermore, MRI based parameters that describe breast physiology have been found to correlate well with immunohistochemically measured angiogenesis markers (Su, 1995; Su, 1994; Su, 1996). *Thus, dynamic contrast enhanced MRI will be used as a secondary surrogate marker in the proposed study.*

Methodology to test the hypothesis: Core biopsies will be obtained from patients whose mammographic findings are suspicious for DCIS. Patient will undergo MRI study prior the biopsy. At the time of biopsy, a portion of the tissue retrieved will be sent in formalin for histopathological examination for Ki-67, ER, PR and angiogenesis markers evaluation.

1 mg of anastrozole administered orally daily for 4 weeks after the diagnosis of DCIS/invasive breast cancer. The reason for using a 4-week regimen is that this is the average time between diagnostic biopsy and definitive lumpectomy or mastectomy.

Patients will undergo MRI at baseline before therapy and then again after anastrozole treatment that will be followed immediately by definitive surgical procedure, i.e. lumpectomy or mastectomy. Lumpectomy/mastectomy specimen will be again evaluated for the level of tumor

Ki-67 decline and the level of angiogenesis markers. The specimen will be subjected to the routine histopathological, and ER and PR evaluation. Histopathological changes pre and post anastrozole will be evaluated in an exploratory analysis.

Detailed Methodology

1. **Quantification of Ki-67 as a Primary Marker to Monitor Response to Chemoprevention by Aromatase Inhibitor Anastrozole**

Measurement of Ki-67 Levels.

[figure not shown]
Measurement of **Ki67** will be performed with the MIB1 mouse monoclonal antibody. To ensure acceptable precision, quantitation of Ki67 will involve the counting of 1000 cells.

Other Tissue Biomarkers.

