An IV line will be set up by placing an indwelling cannula in an antecubital vein before patient is placed into the scanner. The patient will then be placed in the prone position with both breasts hanging in a double breast coil. The following image sequences will be performed.

First a 3D slab covering the entire area of interest will be selected for shimming. The study protocol consists of the following pulse sequences:

T1-weighted spin echo pulse sequence. TR= 928 ms, TE=14 ms, matrix size= 256x256, 32 slice with 4 mm thickness, no gap. The scan time is 3 min 07 s.

Fat Sat T2-weighted pulse sequence. TR= 5930 ms, TE=90 ms, matrix size= 256x252, 32 slice with 4 mm thickness, no gap. The scan time is 3 min 39 s.

3D Turbo Flash pulse sequence for sagittal dynamic imaging. TR= 10 ms, TE=3.0 ms, flip angle = 20-degrees, 24 slices with 5 mm thickness. The scan time is 31.8 s per acquisition. Repeat the sequence 16 times for dynamic acquisition, 4 pre-contrast, and 12 post-contrast. The contrast agent (Magnevist[®], 0.1 mmol/kg) will be calculated based on patient's body weight. The injection starts after 4 pre-contrast acquisitions have been completed, and the total injection time will be fixed at 15 sec, i.e. all contrast agents will be administered at constant rate and finish in exactly 15 sec.

For ease of comparison of the images acquired using different pulse sequences, the number of slices, thickness, and location in all 3 pulse sequences are kept the same.

2.b Image Analysis:

Based on the Gd-DTPA enhanced images at 3 minutes after the injection, the tumor regions will be manually outlined slice by slice. Then the enhancement time course of Gd-DTPA from the tumor ROI in each imaging slice will be obtained. For each tumor a mean enhancement time course will be calculated. Then the data will be analyzed following the procedure described below to generate the pixel population distribution curves of each vascular volume parameter (VB). The enhancement time course of Gd-DTPA will be analyzed with the pharmacokinetic model to derive the parameters for vascular volume (VB) and permeability (K₂) information. In each tumor the analysis will be performed on a pixel-by-pixel basis. After the analyses are completed, the derived parameters from all pixels in an imaging slice will be reconstructed into the parameter maps. From all pixels in each tumor, the pixel population distribution curves of

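### Section 10.2 grades histopathological response by change in size that the baseline core biopsy cannot measure, names no governing scale, and lets tissue removed at biopsy count as response

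*Combined protocol and SAP*

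**What the plan says.** Section 10.2 is headed as histopathological response and gives two kinds of grading.

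- **Size categories.** "A complete response (CR) indicating the disappearance of the primary tumour; a partial response (PR) indicating a reduction of" at least 50%. Stable disease is a smaller reduction or an increase below 25%, and "progressive disease (PD) indicating an increase in size of" 25% or more. No instrument, dimension or baseline measurement is named.
- **Specimen gradings.** "The pathological CR will be evaluated by tumour excision and axillary node resection", the nodes in invasive cases only. Then: "Two grading classifications will be utilised to evaluate the tumour response after chemotherapy". These are Chevallier and Sataloff. As described there, a Chevallier complete response allows in situ disease to persist.

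The Section 9.0 calendar takes diagnosis, ER/PR, Ki-67, angiogenesis markers and "Assessment of Tumor Grade and Histologic Type" from the core biopsy. It has no row for tumour size at any time. MRI is the only lesion imaging scheduled both before and after anastrozole.

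Section 2.0 states, under Specific Aim 2: "The percent ability to reverse early breast cancer lesions in patients treated with anastrozole will be qualified as a secondary surrogate endpoint". It hypothesises a 30-40% response. The paragraph on completion of the aims takes the reversal percentage from the lumpectomy or mastectomy specimen. The methodology paragraph calls the pre/post histopathological comparison exploratory and says of the baseline scan: "Patient will undergo MRI study prior the biopsy".

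**The concern.** A percent change in size needs the same quantity measured twice. Histology cannot supply the first value here, because a core biopsy samples a lesion and does not measure its extent. If the second value comes from the surgical specimen, as the aims paragraph in Section 2.0 indicates, the two values come from different instruments.

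The second problem is attribution. The biopsy removes part of the lesion after the baseline MRI and before the first dose. Section 11.0 expects small tumours. A lesion largely or wholly taken by the needle can meet the definition of partial or complete response without any drug effect. No passage says how such cases are handled.

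At stake are the Aim 2 reversal rate and the correlations of histopathological response with Ki-67, MRI and angiogenesis markers (objectives 1.2 and 1.6). Following Section 10.2 as written could give a wrong rate, so this is more than a missing detail.

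**Working it through.** No sample size, power or significance level in the plan rests on this endpoint, so there is no stated figure to reproduce. The check compares the sections and adds two geometric illustrations.

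**1. Where could the size values come from?**

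| Source | Before | After | Size variable defined? |
|---|---|---|---|
| Histology (9.0, 10.2) | core biopsy | excision specimen | no; baseline size not obtainable |
| Mammography, physical examination (9.0) | yes | not scheduled | no |
| MRI (9.0; Section 2.0, 2.a and 2.b) | yes, before biopsy | yes, before surgery | no; outlines are used for the vascular parameters only |
| Tumour assessment forms (Master Forms Set) | listed | listed | content not in the available text |

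MRI could give a like-for-like comparison, but that would be an imaging response. Objective 1.6 correlates MRI response with histopathological change, so taking the histopathological categories from MRI would partly correlate MRI with itself.

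**2. Does the unstated dimension matter?** Assume uniform change in a round lesion, with diameter ratio r. The changes in diameter, bidimensional product and volume are r − 1, r² − 1 and r³ − 1.

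- 10 to 7 mm (r = 0.7): reductions of 30%, 51% and 65.7%. This is stable disease by diameter and partial response by product or volume.
- 10 to 11.5 mm (r = 1.15): increases of 15%, 32% and 52%. This is stable disease by diameter and progression by product or volume.

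**3. How much could the biopsy remove?** The documents give no core width, core count or distribution of lesion size, so these are assumed. Take a spherical lesion of diameter d and k non-overlapping cores of width c, each crossing it along the mean chord 2d/3:

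fraction = k·π(c/2)²·(2d/3) ÷ (πd³/6) = k·c²/d²

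| d | 3 cores, 1.6 mm | 5 cores, 1.6 mm |
|---|---|---|
| 5 mm | 7.68/25 = 31% | 12.8/25 = 51% |
| 10 mm | 7.68/100 = 8% | 12.8/100 = 13% |
| 20 mm | 7.68/400 = 2% | 12.8/400 = 3% |

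Wider cores raise this. Eight cores of 2.5 mm give 8 × 6.25/d² = 50/d²: all of a 5 mm lesion, 50% at 10 mm and 12.5% at 20 mm.

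These are volume fractions. Under uniform shrinkage a 50% fall in volume is a fall of 1 − 0.5^(1/3) = 20.6% in diameter, so the 51% case would not reach the partial-response limit if size means diameter.

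**4. Does the specimen scale solve the problem for DCIS?** Not fully. The Chevallier tumour criterion, as Section 10.2 states it, is met when in situ disease persists. A patient whose lesion was only DCIS could meet it with no change at all.

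**The case against.** The strongest reply is that this is a clarification of a minor endpoint. Much of it stands.

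- **Unlike instruments.** A reader might infer that the size categories must always compare a specimen with an image. The documents do not support that. Paired MRIs with the tumour outlined slice by slice are scheduled, and the unseen forms may record size. What stands is that the source is not named, and that the instruments differ if the specimen supplies the second value.
- **Specimen gradings.** Chevallier and Sataloff need no baseline size, and the Ki-67 correlation is stated directly after them. That is a fair reading, but Section 10.2 never says that they govern, and it gives the size categories first under the same heading.
- **Size of the biopsy effect.** A reader might give every core the full diameter and obtain 46-77% at 5 mm (k·π·0.8²·5 ÷ (π·5³/6), k = 3 and 5). All diameters cross at the centre, so such cores cannot avoid overlapping. Parallel 1.6 mm cores packed in a ring about the centre give about 41% and 61%; the mean chord gives 31% and 51%.
- **Slice thickness.** The dynamic series has "24 slices with 5 mm thickness", and a reader might conclude that a 2.5 mm change (25% of 10 mm) is beyond its resolution. Slice thickness limits measurement through the plane and says nothing against an in-plane diameter.
- **Lesions wholly removed.** These leave no tumour for a post-treatment Ki-67 and so drop out of the Ki-67 correlation. Section 11.0 already allows for 50% non-evaluability. They can still enter the response rate as complete responses.

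**Conclusion.** The point holds in a limited form. Section 10.2 defines a histopathological endpoint by size change that baseline histology cannot provide, and does not name the measurement or the scale behind the Aim 2 rate and the correlations. Its disappearance criterion can also credit needle removal to anastrozole.

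The biopsy effect depends on lesion size and sampling. Under the thin-core assumption it is about 31-51% of volume at 5 mm, 8-13% at 10 mm and 2-3% at 20 mm. A reader might infer that every response is contaminated; these figures show a risk concentrated in the smallest lesions, and they rest on assumed cores all passing through a spherical lesion.

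A reader might also infer that the trial's main result is affected. It is not: the primary Ki-67 responder test and its sample size do not use this endpoint, which Section 2.0 calls secondary in one place and exploratory in another. The change should be made, but the trial does not depend on it.

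**What to change.** 1. In Section 10.2, apply the four size categories only to the two MRIs already scheduled. State one dimension, for example longest in-plane diameter read the same way both times, and label the result *imaging size response*. State beside it that the baseline MRI precedes the biopsy, so the change includes any tissue removed.
2. Base histopathological response on the excision specimen only. Name the scale used for the Aim 2 rate and for each correlation. Do not count persistent in situ disease as a complete response in patients whose core biopsy showed only DCIS.
3. Where no residual tumour is found and the specimen shows only the biopsy site, report *lesion possibly removed at biopsy* separately from complete response. Give the response rate with and without these patients.

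The cost is a wording change to Section 10.2 and matching entries on the two tumour assessment forms. No new procedure is needed. The MRI size result still contains biopsy removal, which the caveat discloses but does not remove. The histopathological response rate may look less favourable.

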1.0 OBJECTIVE

- 1.1 To assess the efficacy in terms of reduction in Ki-67(as a surrogate endpoint to breast cancer risk reduction) in patients treated with anastrozole.
- 1.2 To measure the histopathological response and correlate the degree of histopathological response with the degree of Ki-67 response.
- 1.3 To compare pretreatment vascular density with post treatment vascular density using MRI
- 1.4 To compare pretreatment markers of angiogenesis with post treatment marker of angiogenesis.
- 1.5 To correlate MR imaging response to markers of angiogenesis response.
- 1.6 To correlate ER, Ki-67, angiogenesis markers and MRI response to histopathological changes

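### The pathological CR rule in Section 10.2 accepts persisting in situ disease and does not clearly exempt DCIS-only patients, so unchanged DCIS can be scored as complete response

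*Combined protocol and SAP*

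**What the plan says.** Specific Aim 2 (Section 2.0) hypothesises that "histopathological tumor response will be demonstrated in 30-40 percent of patients with preinvasive (DCIS) and early invasive (less than 2 cm) breast cancer". It describes the endpoint as reversal: "The percent ability to reverse early breast cancer lesions in patients treated with anastrozole will be qualified as a secondary surrogate endpoint". The summary after the specific aims places the assessment on the lumpectomy or mastectomy specimen.

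Section 10.2 then gives two kinds of response definition.

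- **A size scale.** It opens with "A complete response (CR) indicating the disappearance of the primary tumour". Partial response is a reduction of at least 50%, stable disease (SD) a smaller reduction or an increase below 25%, and progression an increase of 25% or more.
- **Pathological CR.** "The pathological CR will be evaluated by tumour excision and axillary node resection (in case of invasive breast cancer only"). It continues: "Two grading classifications will be utilised to evaluate the tumour response after chemotherapy". Chevallier CR is "the absence of invasive tumour cells, or persistence of" in situ disease, with negative axillary nodes. Sataloff is said to have similar criteria.

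Section 10.2 closes with the planned use: "We will correlate patients with degree of drop of Ki-67 with degree of pathological response". Objective 1.2 likewise sets out to "correlate the degree of histopathological response with the degree of Ki-67 response", and Objective 1.6 relates ER, Ki-67, angiogenesis markers and MRI response to histopathological change.

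Section 5.2 admits patients with either DCIS or early invasive cancer on core biopsy. Section 11.0 defines responders by Ki-67 alone and describes no analysis of histopathological response.

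**The concern.** A rule that tolerates residual in situ disease suits an invasive cancer whose invasive part has gone. It does not suit a patient whose whole lesion was in situ from the start. She meets the tumour part of the rule before her first dose, and meets it again at surgery if nothing has happened. Section 10.2 brings the rule in from the chemotherapy setting, which this trial is not, and does not adapt it to DCIS.

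Aim 2 asks how often early lesions are reversed. A scoring rule that can record non-reversal as complete response works against that question. The response variable is also the one correlated with the fall in Ki-67 and with the angiogenesis and MRI measures, so misclassified patients would distort those correlations too.

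**Working it through.** The 30–40% in Aim 2 has no derivation or sample size behind it, so there is no planned figure to reproduce. The check applies the rules of Section 10.2 to one case and then shows how far the rate can move.

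**Step 1. One case: DCIS only on core biopsy, same DCIS at surgery.**

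- Size scale: the change is 0%, which is a reduction below 50%, so SD.
- Chevallier, tumour part: no invasive cells and in situ disease persists, so met.
- Chevallier, nodal part: negative nodes are required, but nodes are resected for invasive cancer only, so there may be no nodal result.

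**Step 2. Two readings of the restriction to invasive cancer.**

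- *It limits only the node resection.* This is the more natural reading, because the parenthesis directly follows those words. The DCIS-only patient is then judged on the excision. If the nodal part is waived or taken as negative, she is a pathological CR. If it is required, she is not assessable, or is counted as not CR.
- *It limits the whole pathological CR evaluation.* DCIS-only patients are then exempt and have only the size scale, on which this patient is SD.

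**Step 3. Size of the effect if the nodal part is treated as met.**

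Inputs: 24 evaluable patients (Section 11.0, where the number is set for the Ki-67 analysis). DCIS-only share d assumed at 20%, 40% and 60%, because the documents do not give it. Inert drug, all lesions unchanged, so no invasive patient is a CR. Count k = 24 × d, rounded; rate = k/24; exact (Clopper-Pearson) 95% intervals.

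| d (assumed) | k | Pathological CR, up to | CR on size scale |
|---|---|---|---|
| 20% | 4.8 → 5 | 5/24 = 21% (7–42) | 0/24 = 0% (0–14) |
| 40% | 9.6 → 10 | 10/24 = 42% (22–63) | 0/24 = 0% (0–14) |
| 60% | 14.4 → 14 | 14/24 = 58% (37–78) | 0/24 = 0% (0–14) |

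If all 42 accrued patients were assessable, d = 40% would give 17/42 = 40% (26–57) against 0/42 (0–8.4). The rate follows d; the denominator mainly changes the width of the interval.

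**Step 4. Size of the effect if the nodal part is required.**

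There is no false CR, but the denominator is open. If a share x of invasive patients reach pathological CR, the overall rate is x with DCIS-only patients left out and x(1 − d) with them counted as non-responders. With 10 of 24 DCIS only and x assumed at 35%, the two results are 35% (n = 14) and 0.35 × 14/24 = 20.4%.

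**The case against.** The strongest reply is that Section 10.2 already protects against the bad result. Its first definition of CR is disappearance of the primary tumour, and in a DCIS-only patient the primary tumour is the DCIS. The restriction to invasive cancer can also be read as taking DCIS out of pathological CR altogether. A pathologist would probably not call unchanged DCIS a complete response, since that contradicts the aim of reversal.

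Much of this stands as a statement of probable intent. It does not settle the text. The size scale and the pathological CR rule stand side by side, and nothing says which governs the Aim 2 rate. If DCIS is exempt, the two groups have different sets of scales, yet Aim 2 pools them in one rate.

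A second objection is that the illustration rests on an assumed DCIS share and on the nodal part being treated as met for every DCIS-only patient. That is correct, and the figures are upper limits for that handling.

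A reader might also infer that an inert drug would by itself deliver the 30–40% response that Aim 2 predicts. The documents do not support that comparison. Aim 2 backs its figure with foamy-macrophage infiltration and fibrosis in invasive cancers after chemotherapy, and mentions complete pathological response separately. The figure is not shown to be a pathological CR rate.

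Finally, the endpoint is minor: Aim 2 calls it secondary, and the methodology paragraph of Section 2.0 treats histopathological change as exploratory. That limits the weight of the point but does not remove it.

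**Conclusion.** The concern holds in a limited form. As written, Section 10.2 allows unchanged DCIS to be scored as pathological CR, leaves it not assessable, or exempts it, depending on a reading and a nodal rule that the plan does not fix. It would go too far to say that the plan requires unchanged DCIS to be counted as response: the exempting reading is open, and so is requiring the nodal result.

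Under the least favourable handling, with 24 evaluable patients and an assumed DCIS-only share of 20% to 60%, the pathological CR rate for an inert drug could reach 21% to 58%, against 0% complete responses on the size scale. These numbers show how strongly the result depends on the case mix; they do not predict it.

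The consequence is confined to the Aim 2 rate and the correlations in Objectives 1.2 and 1.6. The Ki-67 primary endpoint, its test and the sample size do not use this variable.

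**What to change.** In Section 10.2:

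- State that Chevallier and Sataloff pathological CR apply only to patients with invasive cancer on core biopsy.
- State that persisting DCIS in a DCIS-only patient is not a CR.
- State that a patient with DCIS on core biopsy and invasive disease at surgery is not a CR.
- Name one scale that applies to both groups, assessed on the surgical specimen as the summary of the specific aims says, for the Aim 2 rate and for the correlations in Objectives 1.2 and 1.6. Say which of its categories count as response.
- Report pathological CR in addition, for invasive cases only.

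In Section 11.0, add that the Aim 2 rate is reported separately for DCIS-only and invasive patients, with exact 95% confidence intervals.

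Replacing the specimen assessment with MRI size is not advised. It would turn a histopathology endpoint into an imaging one and make the MRI correlation in Objective 1.6 partly circular.

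The cost is a few sentences. No new procedure is needed for the split, because Section 9.0 already records the diagnosis and histologic type on core biopsy and after surgery. The downsides are that the reported response rate may be lower and that subgroup rates will be imprecise: 4 responders among 10 DCIS-only patients, for example, would be 40% with an exact 95% interval of 12% to 74%.
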